5.2.3. Secondary Endpoints in RI and LTE Period

These include efficacy endpoints in the RI period and the LTE. Since there is no control arm in these 2 periods, only descriptive statistics will be provided. Summary statistics will be generated following the methodologies stated in Section 3.1 using RIS or LTES analysis sets. All time-to-event endpoints start from the first day of receiving riloncept in that period. Unless specified otherwise, the denominator of a response rate or percentage will be the total number of subjects treated in that period.

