5.2.3.1. Secondary Endpoints in the RI Period

The following efficacy endpoints will be included for the RI period. Unless specified otherwise, change means change from RI baseline to RI week 12, and the denominator for a proportion is the total number of subjects who were treated in the RI period.

1. Time to pain response, defined as number of days from first dose to the first day a subject’s daily pain NRS is ≤ 2 of the 3 days over which, the rolling average daily pain NRS is ≤ 2 . Subjects with baseline NRS ≤ 2 will be excluded from the analysis. If one or more daily NRS score is missing, rolling average will be considered not meeting the response criteria.
2. Time to CRP normalization (≤ 0.5 mg/dL)

Time to CRP normalization will be censored at treatment discontinuation, taking prohibited medication, or week 12, whichever occurs first. Subjects with baseline CRP ≤ 0.5 mg/dL will be excluded from the analysis.

3. Time to riloncept monotherapy

Time to riloncept monotherapy is defined as number of weeks from first dose to the first day of achieving monotherapy. Subjects without background therapies at RI baseline will be excluded from the analysis.

4. Time to treatment response defined as time from first dose to the first day of pain response (defined in endpoint 1 above), and CRP ≤ 0.5 mg/dL within 7 days before or after pain response. Treatment response day will be the day of pain response, whether pain response occurs before or after CRP ≤ 0.5 mg/dL.
5. Proportion of subjects achieving clinical response at RI week 12 based on RIS analysis set

Subjects who stopped background SOC pericarditis therapy on or before week 10, as well as who achieve CRP ≤ 0.5 mg/dL and weekly average of daily pericarditis pain score ≤ 2.0 on the 11-point NRS within the 7 days prior to and including the day of randomization on RI Week 12/Randomization are responders.

Additional analysis will be done base done the completers who finished the 12-weeks of RI treatment.

6. Number (percentage) of subjects with normalization of CRP (≤ 0.5 mg/dL) at RI Week 12. Subjects with baseline CRP > 0.5 mg/dL in the RI analysis set will be used in the analysis.
7. Change from baseline in pericarditis weekly pain score at RI Week 12 and over time.
8. Change from baseline in CRP level at RI Week 12 and over time.
9. Proportion of subjects with resolution of echocardiographic and ECG abnormalities (yes/no) at RI Week 12.

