5.2.3.2. Efficacy Endpoints in the LTE Period

The efficacy endpoints below are included in this period. These endpoints will not be included in the primary analysis for the RW period since data will not be available at that time. Each endpoint will be summarized through Week 24 in this period, by subjects who did and did not have an adjudicated pericarditis recurrence in the RW period and by subjects who enter LTE directly from the RI period, respectively, and overall. The baseline for the LTE period will be the last assessment before the first dose in the LTE period.

1. Number (percentage) of subjects with pericarditis recurrences based on investigators' judgement.
2. Proportion of subjects with Clinical Response (riloncept monotherapy + CRP ≤ 0.5 mg/dL + NRS ≤ 2) at each CRP assessment (weeks 12 and 24). The pain NRS at the visit when CRP was assessed will be used.
3. Change over time in CRP levels.
4. Change over time in pericarditis pain NRS.

5. Proportion of subjects with absent or minimal pericarditis symptoms over time based on PGIPS.
6. Proportion of subjects with absent or minimal pericarditis activity over time based on the PGA-PA.
7. Change from baseline in the SF-36 8 domain scores, as well as the physical and mental scores.
8. Change in the SF-6D 6 domain scores and the utility index.
9. Change from baseline in the EQ-5D-5L individual scores and index value.
10. Change from baseline in the subject's sleep quality assessed with the ISI.
11. Change over time in ISI categories.
12. Number (percentage) of subjects requiring addition of SOC pericarditis therapy every 4 weeks cumulatively.
13. Change from baseline in pericardial signs in ECHO, ECG, and MRI.
14. Corticosteroid use over time.

For subjects who are on corticosteroid at RI baseline, the proportion of subjects using corticosteroid at LTE will be summarized. The denominator will be the number of subjects using corticosteroid at RI and entering the LTE. The average daily dose of corticosteroid (mg/day) will be summarized.

15. In the MRI substudy, resolution in pericardial inflammation among subjects with pericardial inflammation at RI baseline as assessed by cardiac MRI. The endpoints below will be summarized.
 - a. Proportion of subjects with pericardial Delayed Hyperenhancement
 - b. Proportion of subjects with Myocardial Delayed Hyperenhancement
 - c. Proportion of subjects with pericardial effusion, and effusion size
16. Annualized recurrent rate during treatment

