c Full physical examination includes at minimum evaluation of vital signs, head, eye, ear, nose, and throat as well as cardiovascular, dermatological, musculoskeletal, respiratory, GI, genitourinary, and neurological systems. The decision to perform examination of genitourinary system should be guided by clinical judgement.

d Abbreviated physical examination includes at minimum evaluation of vital signs, lung and heart sounds, including evaluation for pericardial rub.

e ECHO is required to be obtained according to the central core lab parameters and then read locally and submitted to the central core lab for separate review and analysis.

f Both a documented CRP ≥ 1.0 mg/dL AND a pericarditis pain level of ≥ 4 is required 7 days prior to and including the Run-In Baseline visit. These are not required to occur on the same day.

g Subjects missing ≥ 4 daily pain measurements during the 7 days prior to and including the Randomization Withdrawal baseline visit will be unable to proceed to randomization due to lack of data required for treatment response evaluation.

h Lipid panels are non-fasting and are to be drawn at a minimum of every 6months during the randomization withdrawal and LTE periods, or more frequently as needed, with mandated evaluations as detailed in the schedule of events.

i Applicable to 24-hour post dose PK sub-study participants only.

j For women of child bearing potential - urine pregnancy testing can be repeated as needed throughout the course of the study and serum pregnancy can be drawn as needed; urine pregnancy is required to be performed at enrollment and 6 weeks after the last dose of study drug.

k Pharmacogenomics informed consent and subsequent sampling can be performed at any time in the study however, it is preferable to have this completed at the beginning of the study.

l Adverse event reporting begins following the subject providing informed consent.

m All procedures are to be completed prior to study drug administration.

Statistical Analysis Plan

Kiniksa Pharmaceuticals, Ltd.
Study KPL-914-C002

-
- n The first dose of study drug is a loading dose. Adult subjects receive 2 SC doses 160 mg (total 320 mg); pediatric subjects (subjects ≥ 12 and < 18 years of age) receive 2 SC doses of 2 x 2.2 mg/kg.
 - o Study drug administration is once weekly with a minimum of 5 days required between doses.

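### Run-in endpoint 9, resolution of echo and ECG abnormalities, takes all treated subjects as its denominator, so it is not a resolution rate

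*SAP*

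**What the plan says.** All references are to SAP v2.0.

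- **Endpoint.** Section 5.2.3.1, item 9, is a single line: "Proportion of subjects with resolution of echocardiographic and ECG abnormalities (yes/no) at RI Week 12". It gives no baseline condition, no coding of the yes/no result, and no statement on whether echo and ECG are taken jointly or separately.
- **Default denominator.** The opening paragraph of Section 5.2.3.1 states that, unless an item says otherwise, "the denominator for a proportion is the total number of subjects who were treated in the RI period". The parent Section 5.2.3 has the same rule: "Unless specified otherwise, the denominator of a response rate or percentage will be the total number of subjects treated in that period".
- **Items that do restrict.** RI endpoint 6 (CRP normalisation) takes only subjects whose baseline CRP was above 0.5 mg/dL "in the RI analysis set will be used in the analysis". In Section 5.2.3.2, LTE endpoint 15 is framed as "resolution in pericardial inflammation among subjects with pericardial inflammation at RI baseline as assessed by cardiac MRI".
- **Baseline status.** Footnote f to Table 4 (Section 13.1) asks for a documented CRP of at least 1.0 mg/dL "AND a pericarditis pain level of" at least 4, and mentions no echo or ECG finding. Section 5.1.3 lists effusion, ST-elevation, PR-depression and ECG interpretation among the baseline characteristics to be tabulated as counts and percentages, that is, as features some subjects have and others do not.

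**The concern.** Resolution can occur only in a subject who had the abnormality. A proportion labelled as resolution but divided by everyone treated mixes two quantities: how many subjects had something to resolve, and how many of those resolved. Because this denominator follows from a stated rule, the problem is more than missing detail: a programmer who follows the SAP exactly produces a figure that does not match its label.

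This is the RI endpoint on whether objective echo and ECG signs clear by Week 12. It will be read next to CRP normalisation (endpoint 6), which is confined to affected subjects, so the two percentages would not be comparable.

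**Working it through.** **Plan's own figure.** The SAP states no figure for this endpoint, so there is none to reproduce.

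**Inputs**
- N = 56, the planned enrolment in Section 2.3.1. It follows from 50 randomised with 10% not reaching randomisation: 50 / 0.90 = 55.6, rounded up to 56. It is used only for illustration.
- n = subjects abnormal at RI baseline. The SAP gives no value, so a prevalence of 10% to 100% is assumed.
- k = subjects among those n who resolve by Week 12. The SAP gives no value; about 80% of n is assumed, rounded to whole subjects.

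**Formulas**
1. Rate among affected subjects: k / n.
2. All treated, normal at baseline coded no: k / N = (n / N) × (k / n). Since k ≤ n, this cannot exceed the prevalence n / N.
3. All treated, normal at baseline coded yes: (k + N − n) / N. This cannot fall below 1 − n / N and is never lower than k / n.

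**Results**

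| Assumed prevalence | n | k | Among affected, k/n | All treated, normal = no | All treated, normal = yes |
|---|---|---|---|---|---|
| 10% | 6 | 5 | 83.3% | 5/56 = 8.9% | 55/56 = 98.2% |
| 25% | 14 | 11 | 78.6% | 11/56 = 19.6% | 53/56 = 94.6% |
| 50% | 28 | 22 | 78.6% | 22/56 = 39.3% | 50/56 = 89.3% |
| 75% | 42 | 34 | 81.0% | 34/56 = 60.7% | 48/56 = 85.7% |
| 100% | 56 | 45 | 80.4% | 45/56 = 80.4% | 45/56 = 80.4% |

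**The cap.** Even if every abnormality resolved, the no coding would give at most 6/56 = 10.7% at 10% prevalence, 14/56 = 25% at 25%, and 28/56 = 50% at 50%.

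**Convergence.** Both all-treated figures approach the rate among affected subjects as prevalence rises, and equal it at 100%. The last row is the only one in which the SAP's denominator gives a resolution rate.

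**The case against.** The strongest points on the other side are these.

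- **Direction.** A reader might infer that the endpoint simply reports prevalence times resolution and so understates. The SAP does not support that: it holds only if subjects normal at baseline are coded no. That is the natural reading of the word, but the yes/no coding is undefined, and the opposite coding overstates.
- **Size.** A reader might also infer that the percentage depends mainly on how many subjects were abnormal at entry. The SAP gives no prevalence. Subjects enter with an active episode, and nothing in the SAP favours a low value over a high one.
- **Recoverability.** Section 5.1.3 requires baseline effusion and ECG counts, and Section 5.3.4 an ECG shift table. Under the no coding a reader could go some way towards the conditional rate. This stands in part. However, the shift table runs to the last post-baseline assessment rather than RI Week 12 and omits echo. The echo shift tables (Section 5.2.2.3, endpoint 13) start at the randomised-withdrawal baseline. None of these sets the denominator of endpoint 9.
- **Comparators.** RI endpoints 1 to 3 also exclude subjects already at target; endpoint 3, for example, says "Subjects without background therapies at RI baseline will be excluded from the analysis". But they are time-to-event endpoints, where such exclusions are usual. RI endpoint 18 (off background medication) keeps the whole RI analysis set. So the SAP has no uniform convention that endpoint 9 alone breaks. The apt comparators are RI endpoint 6 and LTE endpoint 15, and those stand.
- **Joint wording.** Echo and ECG may be meant as a list reported by modality, as in LTE endpoint 13. That is possible but not stated, and one added phrase settles it.
- **Protocol.** The protocol is not at hand and may say more. The SAP nevertheless fixes a denominator itself, and Section 11.1 records no departure for this endpoint.
- **Importance.** Section 5.2.3 limits RI endpoints to descriptive statistics, and endpoint 9 is outside the testing hierarchy in Section 3.3. This stands and limits the severity.

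**Conclusion.** The point holds. Followed as written, endpoint 9 divides resolution by all treated subjects, including any with no abnormality at RI baseline, and the result is not a resolution rate under either coding. With an assumed 25% prevalence, 56 treated and 11 of 14 resolved, the same data give 19.6% or 94.6% against 78.6%.

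The structural error needs only one condition: that some treated subjects have a normal echo or ECG at RI baseline. The baseline requirement shown in the SAP (pain and CRP) and the tabulation of these findings as variable both point that way. The size and direction of the error cannot be fixed from the SAP, because both the prevalence and the coding are missing.

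Severity is minor to moderate. No hypothesis test, error rate, or primary or major secondary result depends on this endpoint.

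**What to change.** Add a clause to RI endpoint 9, for example:

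> Summarised separately for echocardiographic and for ECG abnormalities. For each, the denominator is the number of subjects in the RI analysis set who had that abnormality at RI baseline; this number will be reported.

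This matches the approach of RI endpoint 6 and LTE endpoint 15. It needs no new data: Table 4 already schedules echo and ECG at RI baseline and at RI Week 12.

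Two further choices are optional and not required by this point: how to count a missing Week 12 reading (Section 3.5 already sets observed data as the general rule), and whether to name specific findings such as effusion or ST/PR changes.

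The cost is smaller denominators and less precision: at an assumed 25% prevalence, 14 subjects rather than 56. Reporting the number affected makes that visible.

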5.2.3.2. Efficacy Endpoints in the LTE Period

The efficacy endpoints below are included in this period. These endpoints will not be included in the primary analysis for the RW period since data will not be available at that time. Each endpoint will be summarized through Week 24 in this period, by subjects who did and did not have an adjudicated pericarditis recurrence in the RW period and by subjects who enter LTE directly from the RI period, respectively, and overall. The baseline for the LTE period will be the last assessment before the first dose in the LTE period.

1. Number (percentage) of subjects with pericarditis recurrences based on investigators' judgement.
2. Proportion of subjects with Clinical Response (riloncept monotherapy + CRP ≤ 0.5 mg/dL + NRS ≤ 2) at each CRP assessment (weeks 12 and 24). The pain NRS at the visit when CRP was assessed will be used.
3. Change over time in CRP levels.
4. Change over time in pericarditis pain NRS.

5. Proportion of subjects with absent or minimal pericarditis symptoms over time based on PGIPS.
6. Proportion of subjects with absent or minimal pericarditis activity over time based on the PGA-PA.
7. Change from baseline in the SF-36 8 domain scores, as well as the physical and mental scores.
8. Change in the SF-6D 6 domain scores and the utility index.
9. Change from baseline in the EQ-5D-5L individual scores and index value.
10. Change from baseline in the subject's sleep quality assessed with the ISI.
11. Change over time in ISI categories.
12. Number (percentage) of subjects requiring addition of SOC pericarditis therapy every 4 weeks cumulatively.
13. Change from baseline in pericardial signs in ECHO, ECG, and MRI.
14. Corticosteroid use over time.

For subjects who are on corticosteroid at RI baseline, the proportion of subjects using corticosteroid at LTE will be summarized. The denominator will be the number of subjects using corticosteroid at RI and entering the LTE. The average daily dose of corticosteroid (mg/day) will be summarized.

15. In the MRI substudy, resolution in pericardial inflammation among subjects with pericardial inflammation at RI baseline as assessed by cardiac MRI. The endpoints below will be summarized.
 - a. Proportion of subjects with pericardial Delayed Hyperenhancement
 - b. Proportion of subjects with Myocardial Delayed Hyperenhancement
 - c. Proportion of subjects with pericardial effusion, and effusion size
16. Annualized recurrent rate during treatment

Annualized recurrent rate will be calculated for subjects randomized to KPL-914 utilizing pooled data in RW and LTE periods and there will be no hypothesis testing.

5.3. Safety Analysis

The following safety endpoints will be analyzed:

- Adverse events,
- Clinical laboratory parameters,
- Serology parameters,
- Hematology parameters,
- Non-fasting lipid panel,
- Pregnancy test,
- Vital signs,

- Urinalysis,
- Electrocardiogram, and
- Physical examination.

Descriptive statistics will be used to summarize safety endpoints for all subjects by the following periods:

- RI period (KPL-914)
- RW period
 - KPL-914 vs. Placebo Including Bailout Rilonecept
 - KPL-914 vs. Placebo before Bailout Rilonecept
- LTE period
- Study overall (RI through LTE), KPL-914 or placebo, regardless of receiving bailout Rilonecept.

Two-sided 95% CIs will be presented where meaningful. Data summaries will be displayed for clinical laboratory analyses, vital signs measurements, ECGs, and physical examination findings.

5.3.1. Adverse Events

Treatment-emergent AEs (TEAEs), defined as AEs that start or increase in severity after the first dose of study drug and before 6 weeks after the last dose of study drug, will be coded to system organ class and preferred term using MedDRA v21.1.

TEAEs will be summarized by each period and study overall. In the RW period, they will also be summarized by including and excluding bailout rilonecept, respectively. The average follow-up duration in weeks for TEAE will be provided in summary tables. The duration of follow-up for each subject is defined as follows.

- For the RI period, it is from first dose in RI period until the day before randomization, last dose day plus 6 weeks, last study day, or data cutoff, whichever occurs first.
- For the RW period including bailout, it is from randomization to data cutoff, last dose day plus 6 weeks, or last study day, whichever occurs first.
- For the RW period before bailout, it is from randomization to the start of using bailout rilonecept, data cutoff, last dose day plus 6 weeks, or last study day, whichever occurs first.
- For the LTE period, it is from first dose day in LTE period to data cutoff, last dose day plus 6 weeks, or last study day, whichever occurs first.
- For study overall, it is from first dose day in RI period to data cutoff, the last dose plus 6 weeks, or last study day, whichever occurs first.

A summary of the frequency (number and percentage of subjects) of TEAEs will be presented by system organ class and preferred term. Adverse events will also be analyzed by their severity (mild, moderate or severe), relationship to study drug, serious AEs, AEs leading to death, AEs resulting in dose interruption, AEs leading to withdrawal of study treatment, and AEs of injection site reaction.

Any AE of malignancy (excluding basal cell carcinoma of the skin) is of special interest. AE of special interest will also be summarized.

A subject experiencing the same AE multiple times will be counted only once for that preferred term. Similarly, if a subject experiences multiple AEs (preferred terms) within the same system organ class, then that subject will be counted only once for that system organ class. When summarizing by severity and relationship, only event with highest severity or relationship will be counted. All AEs will be presented by SOC and preferred terms.

Incidence rate per 100 subject-years and its 95% CI will be calculated by the periods defined for follow-up duration above for the following groups of AEs:

- All AEs (include any AE),
- SAE (include any SAE),
- deaths,
- all infections (including serious),
- serious infections (serious only),
- all ISR (injection site reaction, including serious and non-serious),
- only serious ISR,
- all malignancies excluding NMSC (Non-Melanoma Skin Cancer: ie. cutaneous basal cell carcinoma and cutaneous squamous cell carcinoma).

Incidence rate per 100 subject-years = $100 \times (\text{number of different AE start days within the treatment period}) / (\text{Sum of treatment duration in years from all subjects in the cohort})$.

Multiple events within a subject will be counted as multiple events. Treatment exposure duration and follow-up of AE's in the Study Overall period will be 6 weeks after the last dose. There will be no formal hypothesis testing.

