2. ADDITIONAL ANALYSES

2.1 LTE 18-Month

LTE 18-month is the visit at 18 months after their most recent recurrence, (i.e., the qualifying episode for their original study enrollment prior to enrolling in the RI period or a recurrence in RW which was treated with bailout rilonacept, whichever is the later).

If LTE 18-month visits are collected in CRF, those visits in CRF will be used for analyses. Otherwise, LTE 18-month visits will be mapped based on the visit date on LTE 18-month disposition with 60 days window. The closest assessments will be mapped. If two visits have the same distance, the later one will be used.

In addition to treatment disposition and study disposition, disposition of LTE 18-month will be summarized as well:

- Continue treatment with open-label KPL-914
- Continue in study off-treatment for observation (with option to re-initiate open-label KPL-914 on-study if there is a pericarditis recurrence)
- Discontinue from the LTE
 - Patient decision
 - Investigator's decision
 - No inflammation on MRI
 - Other

For subjects who decided to continue in study off-treatment for observation, the following parameters will be summarized:

- Time on observation: defined as minimum (first dose date after observation-1, EOS date) – disposition date of off-treatment for observation +1.
- Days on treatment before entering observation, defined as: (disposition date of off-treatment for observation-1) - first dose date of LTE period +1.
- Days on treatment after observation for subjects who entered observation and later resumed treatment: minimum (last dose date after observation +6, EOS date) - first dose date after observation + 1.

For the subgroups of subjects who decided to continue in study off-treatment for observation and subjects continue treatment with open-label KPL-914, additional analyses will be conducted.

- Time to recurrence from LTE 18-month will be defined from LTE 18-month disposition date to recurrence or censored at last assessment before treatment resumed or end of study whichever is first.
- Annualized incidence of recurrence after LTE 18-month visit will be defined as number of recurrences for all patients divided by sum of subject-years for all patients within each subgroup. Denominator will be calculated as below:

For subjects who decided to continue in study off-treatment for observation

- If subjects resumed treatment, first dose date after observation period – LTE 18-month disposition date

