2.2 Adverse Events

Two additional summaries of adverse events will be conducted:

- In addition to summarizing treatment-emergent adverse events, post-treatment adverse events will also be summarized. Post-treatment adverse events are defined as adverse events that started after the last dose of study drug in LTE period + 6 weeks.
- Upper respiratory infection adverse events will be summarized. Upper respiratory infection will be identified by the following preferred terms: Nasopharyngitis, Pharyngitis, Pharyngitis streptococcal, Rhinitis, Sinusitis, Upper respiratory tract infection and Viral upper respiratory tract infection.

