5.1.6. Study Drug Administration

The study medication administration details including the administration date and time, dose, site of injection and comments will be presented in a by-subject listing.

The following parameters related to study drug administration will be summarized for each of the treatment periods: RI, RW, LTE, and Study Overall.

- Treatment duration in weeks:
 - For RI period, it is defined as [minimum of (date of last study drug +6, date of RI week 12 visit – 1, date of data cutoff) - date of first study drug + 1)/7].
 - For RW period it is defined as [minimum of (date of last study drug +6, date of end of RW visit) - date of first study drug + 1)/7].
 - For LTE and study overall, it is defined as [minimum of (date of last study drug +6, end of study date, date of data cutoff) - date of first study drug + 1)/7].

Number of administrations in each period regardless of full amount or partial amount of syringe injected. The loading dose includes two injections and will be counted as one administration.

Compliance (%) in each period, calculated as (number of administrations) / (protocol planned number of administrations) × 100%. The loading dose includes 2 injections and will be counted as one administration.

Total riloncept dose administered in each period, defined as the sum of all doses (mg) received in the corresponding period. The actual volume administered will be used to calculate the total dose. For subjects receiving weight-adjusted dose (e.g., 2.2 mg/kg) their weight collected at scheduled visits will be used to calculate the amount of the study drug received.

Percentage of self-administrations by the subject, defined as [Number of self-administrations] / [Total number of administrations received] × 100%. The loading dose will be included in the denominator as one administration. If one of 2 injections in the loading dose is self-administered, it will be counted in the numerator.

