b Scheduling of visits within visit windows requires cautious planning to ensure there is no interruption to subject evaluation and study drug treatment.

c Full physical examination includes at minimum evaluation of vital signs, head, eye, ear, nose, and throat as well as cardiovascular, dermatological, musculoskeletal, respiratory, GI, genitourinary, and neurological systems. The decision to perform examination of genitourinary system should be guided by clinical judgement.

Statistical Analysis Plan

Kiniksa Pharmaceuticals, Ltd.
Study KPL-914-C002

-
- d Abbreviated physical examination includes at minimum evaluation of vital signs, lung and heart sounds, including evaluation for pericardial rub.
 - e ECHO is required to be obtained according to the central core lab parameters and then read locally and submitted to the central core lab for separate review and analysis.
 - h Lipid panels are non-fasting and are to be drawn at a minimum of every 6months during the randomization withdrawal and LTE periods, or more frequently as needed, with mandated evaluations as detailed in the schedule of events.
 - j For women of child bearing potential - urine pregnancy testing can be repeated as needed throughout the course of the study and serum pregnancy can be drawn as needed; urine pregnancy is required to be performed at enrollment and 6 weeks after the last dose of study drug.
 - l Adverse event reporting begins following the subject providing informed consent.
 - m All procedures are to be completed prior to study drug administration.
 - o Study drug administration is once weekly with a minimum of 5 days required between doses.
 - s PK and ADA samples will be collected prior to study drug administration. PK at enrollment/baseline will be taken from ADA. As required, ADA samples will be collected at EOS, ET, and Unscheduled visits.
 - t The EORW visit serves as both the last visit of the RW period and the baseline visit of the LTE period.
 - u For all subjects, the final clinic visit of the end of RW period is to be scheduled once the End of the Randomization Withdrawal end date is announced by Sponsor. This includes subjects that are taking blinded study drug, open-label rilonacept, or who have prematurely discontinued study drug.
 - v Study drug administration to occur only after subject provides informed consent for the open-label extension period.

Table 6: Study Schedule of Activities – Long Term Extension

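### The AE follow-up windows let open-label LTE time into the randomized arms and, for subjects who restart drug, count off-drug observation as treatment-emergent

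*SAP*

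**What the plan says.** **RW windows (SAP v2.0, 5.3.1).** The window with bailout included reads "For the RW period including bailout, it is from randomization to data cutoff, last dose day plus 6 weeks, or last study day". The window before bailout reads "it is from randomization to the start of using bailout rilonecept, data cutoff, last dose day plus 6 weeks, or last study day". Neither lists the EORW visit or the first LTE dose as a stop. By contrast, the run-in window in the same list stops on the day before randomization, and RW treatment duration in 5.1.6 stops at the end-of-RW visit.

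**When open-label drug can start.** Under Section 13.1, Table 5, the EORW visit is also LTE baseline. Footnote v permits dosing there: "Study drug administration to occur only after subject provides informed consent for the open-label extension period". Section 2.4 sets data cutoff only once every subject has had the EORW assessment.

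**LTE windows.** AE follow-up: "it is from first dose day in LTE period to data cutoff, last dose day plus 6 weeks, or last study day". LTE treatment duration (5.1.6): "For LTE and study overall, it is defined as [minimum of (date of last study drug +6, end of study date, date of data cutoff", counted from the first dose. The addendum (2.2) adds a further category: "Post-treatment adverse events are defined as adverse events that started after the last dose of study drug in LTE period + 6 weeks".

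**Planned interruption.** Addendum 2.1 makes off-treatment observation, with restart on recurrence, an option at the 18-month review. It even defines a quantity for "Days on treatment after observation for subjects who entered observation and later resumed treatment". It does not carry that split into the AE windows, and addendum 3.2 keeps safety summaries by study period only.

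**The concern.** An AE table by arm or period is useful only if each event, and the person-time behind it, belongs to the treatment state named in the column. Two of the stated rules break that.

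- **RW.** A subject randomized to placebo who finishes RW without recurrence and takes open-label rilonacept at EORW still has an open RW window. An AE on active drug can then be counted in the placebo-before-bailout column, the cleanest controlled safety comparison in the plan.
- **LTE.** Because everything runs to the last LTE dose, the class of an AE during observation depends on whether the subject later relapses and restarts. An AE 20 weeks off drug is post-treatment in a subject who stays off, and treatment-emergent in one who restarts later. The new post-treatment table loses that part of the restarters' off-drug experience, and the on-treatment table gains it.

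**Working it through.** The plan states no figure on this point, so there is none to reproduce. The check is date logic, followed by illustrations with assumed durations.

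**1. RW overlap per subject**

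Overlap = min(data cutoff, last dose + 42 days, last study day) − first LTE dose date.

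It is positive for a subject who starts LTE drug before cutoff, provided the other two limits fall after that dose. What limits it depends on how last dose is read, which the RW bullets do not say:

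- Last dose in RW: weekly dosing puts it about 7 days before EORW (assumed), so the tail reaches at most about 42 − 7 = 35 days past EORW.
- Last dose overall: only data cutoff or last study day limits it.

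At the primary analysis, cutoff is the practical limit. Table 5 gives EORW a window of ±7 days, so visits held within it differ by up to 14 days. The share of a subject's RW window that is LTE drug time is overlap / (RW days + overlap):

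| Weeks in RW (assumed) | 7-day overlap | 14-day overlap |
|---|---|---|
| 8 | 7/63 = 11.1% | 14/70 = 20.0% |
| 16 | 7/119 = 5.9% | 14/126 = 11.1% |
| 24 | 7/175 = 4.0% | 14/182 = 7.7% |

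**2. LTE follow-up for a restarter**

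Let A = weeks from first LTE dose to last pre-observation dose, G = weeks from that dose to the restart dose, and R = weeks from the restart dose to the final dose. The tail is 6 weeks (5.3.1).

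- As written: A + G + R + 6.
- By treatment spell, each with its own tail: A + min(G, 6) + R + 6.
- Excess: max(0, G − 6).

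With A = 52 and R = 12 (assumed), the written window is 70 + G:

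| G (assumed) | As written | By spell | Excess | Share of written window |
|---|---|---|---|---|
| 6 | 76 | 76 | 0 | 0% |
| 8 | 78 | 76 | 2 | 2.6% |
| 12 | 82 | 76 | 6 | 7.3% |
| 26 | 96 | 76 | 20 | 20.8% |
| 39 | 109 | 76 | 33 | 30.3% |

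**3. LTE treatment duration as a rate denominator**

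Section 5.3.1 says that AE rates are calculated by the follow-up periods, but its formula divides by treatment duration, which in 5.1.6 ends 6 days, not 6 weeks, after the last dose. That duration also spans the gap. Leaving out the one-week tails, it is 52 + G + 12 = 76, 90 or 103 weeks for G = 12, 26 or 39, against 52 + 12 = 64 dosed weeks. For such a subject, a rate of events that occur only on drug, such as injection site reactions, is multiplied by 64/76 = 0.84, 64/90 = 0.71 or 64/103 = 0.62. Counting 7 days for the last dose of each spell gives 66/77 = 0.86, 66/91 = 0.73 and 66/104 = 0.63.

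**The case against.** **RW.** The plan does have a period boundary: AEs are summarized by period, EORW is labelled the last RW visit, and 5.1.6 ends RW treatment duration there. A programmer might apply that boundary unprompted. This limits the likely harm, but the AE windows are written out separately, rates are tied to them, and they omit the stop.

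A reader might infer that the same AE is counted twice in the primary analysis. It is not: Section 2.4 leaves LTE summaries out of that analysis. Double counting would need RW AE tables to be rerun at study end, which the documents do not say will happen. A reader might also fault the bailout-included table for showing active-drug events under placebo. That is its design; the unintended contamination is in the before-bailout table, from subjects who never used bailout.

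**LTE.** Only restarters are affected, and only beyond 6 weeks off drug. The documents do not say how many restart or how long gaps last. The plan's only off-drug recurrence figure is the planning median of 8 weeks on placebo, exponential (2.3.1), in a different setting. Under it, 0.5^(12/8) = 35% of gaps would exceed 12 weeks and 0.5^(39/8) = 3% would exceed 39. The 30% figure is therefore one end of an assumed range, not an expected dilution of the whole LTE table.

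Nor does the post-treatment table lose all of the restarters' off-drug events. The first 6 weeks off drug are treatment-emergent under either rule, and events after the final dose plus 6 weeks are still captured.

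**Weight.** The safety analyses are descriptive, without formal testing, and dosing is listed by subject. All of this limits the size; none of it corrects the rules.

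**Conclusion.** Both defects follow from the rules as written, and nothing in SAP v2.0 or the addendum corrects them.

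- **RW:** a missing stop date allows open-label AEs into the randomized arm's window. At the primary cutoff the overlap is probably days to a few weeks per subject, assuming EORW visits stay near the announced date. It could be larger only if RW tables are rerun later, and by how much depends on the unresolved meaning of last dose.
- **LTE:** misclassified time is max(0, gap − 6 weeks) per restarter, and zero for everyone else. The 7% to 30% range is per affected subject and rests on assumed durations. The total effect cannot be computed from the documents.

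No efficacy result or error rate is touched. The point should be corrected because safety is the study's secondary objective, the misattribution is tied to relapse, and the remedy is cheap.

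**What to change.** (a) **RW, 5.3.1.** Add the day before the first LTE dose to the stopping dates of both RW windows, and state that last dose means the last dose in that period. At the primary analysis, AEs after the first LTE dose then leave the RW tables and can be shown in listings until the LTE is summarized.

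(b) **LTE, 5.3.1 and addendum 2.2.** For restarters, split the LTE into treatment spells. Each spell's treatment-emergent window ends at its last dose plus 6 weeks or the day before the next spell's first dose, whichever comes first. This also handles gaps of 6 weeks or less. AEs between spells and outside these windows are classed as post-treatment (off-treatment observation). Take the actual last pre-observation dose from the dosing records; the addendum's observation derivations start from the disposition date, which need not coincide with it.

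(c) **Durations, 5.1.6 and 5.3.1.** Compute follow-up as the sum of spells with 6-week tails and treatment duration as the sum of spells with 6-day tails. State which one each rate uses, and count in the numerator only events inside that same time.

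Cost: wording in the SAP and addendum and a small derivation change. The administration dates are already collected, so no new data are needed.
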